#### 8.4.2 Data Analysis for Safety

All AEs will be coded using the Medical Dictionary for Regulatory Activities® (MedDRA) v17.0 or higher. The incidence of AEs (new or worsened) will be summarized by primary system organ class, preferred term, severity, and relationship to study intervention. The incidence of death, SAEs, and AEs leading to discontinuation will be summarized separately by primary system organ class and preferred term.

### 8.4.3 Analyses for Exploratory Objectives and Endpoints

Adherence with AMPHORA usage during study (rate of product use adherence) will be measured by inspection/analysis of returned gel applicators and eDiary data. Summary statistics of adherence overall and by intervention group will be provided.

Based on the adherence rate for each subject, sensitivity analyses will be conducted in the same manner as the primary and secondary endpoint analyses to examine if the level of re-infection between treatment groups differs for  $\geq 20\%$ ,  $\geq 40\%$ ,  $\geq 60\%$ , and 100% adherence rates. These sensitivity analyses will be performed on the mITT population.

Subject satisfaction with the study drug (including sexual satisfaction in **Appendix E**) will be summarized using frequency and percentage.

Subject sexual satisfaction will be measured utilizing baseline and follow-up questions on the impact of study drug on sexual function with the SFQ and item 10 on the FSFI. These scores and responses will be summarized using frequency and percentage.

### 9 Data Handling/Recordkeeping/Source Documents

It is each Investigator's responsibility to ensure that all team members appropriately handle all data and related documentation. All subject information, including source documents and laboratory reports, must be reviewed by the Investigator and clinical team and submitted to the ICON GPHS Data Management Team via eCRF. ICON GPHS Data Management will work with the Investigators and CRAs to develop a data management plan, including eCRF creation and instructions for the study to establish, maintain, and update the study data effectively. Clinical data will be entered directly from the source documents to the data management system within 72 hours of study activity to maintain up-to-date information on all clinical and laboratory data. There will be ongoing processing of data and quality checks. CRAs will be responsible for source verification of the eCRFs.

Data security is of paramount concern. A comprehensive IT Systems Security Plan with a disaster recovery plan is in place to safeguard data systems related to this clinical study.

### 9.1 Data Capture Methods

Clinical data (including AEs and concomitant medications) will be entered into the Clinical Studio EDC system. This system is a 21 CFR 11-compliant internet data entry system provided by the ICON GPHS Data Coordinating Center. Only those who are trained and delegated the responsibility by the Investigator (with delegation documented on the signature delegation log) will collect and enter data. The data system includes password protection and internal quality checks, such as heuristic checks, to identify data that appear inconsistent, incomplete, or inaccurate.

#### 9.2 Types of Data

Data for this study will include reported symptoms, AEs, clinical laboratory data, adherence with AMPHORA usage from eDiary data and applicator staining, and clinician-obtained baseline pH values.

Clinical data will be entered directly from the source documents. CRAs will perform source verification and query generation. CRAs will work with the Data Manager and site personnel to freeze data prior to analysis. AEs, medical history, and medications will be coded using MedDRA v17.0 (or higher) and WHO drug dictionaries.

#### 9.3 Study Records Retention

Each study site will maintain appropriate medical and research records for this study, in compliance with ICH E6 R1 Section 4.9, regulatory and institutional requirements for the

protection of confidentiality of subjects. The study site will permit authorized representatives of Evofem, Inc., ICON GPHS, and regulatory agencies to examine (and when required by applicable law, copy) clinical records for the purposes of clinical site monitoring, quality assurance reviews, audits, and evaluation of the study safety and progress. A site master file will be maintained to include essential documents.

Study documents will be retained for a minimum of two years after the last marketing application approval or two years from the formal discontinuation of clinical development of the investigational product. These documents will be retained for a longer period, if required by local regulations. No record will be destroyed without the written consent of Evofem, Inc.

#### 9.4 Source Documents

The source document is defined as the first place the data are recorded, eg, hard copy paper and/or electronic forms, laboratory printouts, and medical records. The study sites may use study-specific paper data collection forms that mirror each EDC form to enter data from the source (the subject's chart, eDiary data, or other medical records) onto the form provided. Clinical and research laboratory reports will be printed from the laboratory system and utilized as source documents. Clinical data will be entered directly from the source documents to the data management system within 72 hours of study activity to maintain up-to-date information on all clinical and laboratory data protocol deviations.

#### 9.5 Protocol Deviations

A protocol deviation is any noncompliance with the clinical study protocol or GCP requirements. The noncompliance may be either on the part of the subject, the Investigator, or the study site staff. As a result of deviations, corrective actions are to be developed by the site and implemented promptly.

Investigation of the protocol deviations will be conducted by the study team, especially the Investigator, to assess whether the deviation is due to a subject-specific issue, or whether there is an underlying structural or operational aspect of the research process and protocol which may require correction or revision.

It is the responsibility of the Investigator to use continuous vigilance to identify and report deviations by entering the information into the clinical database within three working days of identification of the protocol deviation or of the scheduled protocol-required activity. Appropriate reporting forms must be maintained in the regulatory file as well as in the subject's source document. The Investigator is responsible for ensuring all study staff understand the IRB reporting guidelines and adhere to all related requirements and documentation. A cumulative list of protocol deviations will be reported in the clinical study report.

Refer also to Section 10 Quality Control and Quality Assurance.

### 10 Quality Control and Quality Assurance

The Clinical Quality Management Plan (CQMP) is developed by ICON GPHS. The CQMP outlines quality control (QC) and quality assurance (QA) processes to be applied to protocol activities at the clinical sites.

The ICON GPHS QA Specialist will develop, implement, and oversee all functions of the CQMP. The Investigators are responsible for the oversight and implementation of the CQMP at their respective clinical sites. The site roles and responsibilities are to submit protocol deviation logs, AE/SAEs, and screening and enrollment logs within required time intervals.

The QC of study-related records will be performed by the site's clinical staff. Prior to data entry, study visit documentation will be reviewed for accuracy and completeness.

Through periodic verification of data collected for this protocol, ICON GPHS QA activities document compliance with GCP standards, human subjects' protections, and applicable federal regulations governing the use of investigational products. Key quality indicators, as detailed in the CQMP and applicable to the protocol, will be examined in each subject record selected for QA review.

Study records will remain onsite in a secure location. The clinical site will permit ICON GPHS, the Sponsor, and other applicable regulatory authorities access to study-related records.

### 11 Ethics/Protection of Human Subjects

#### 11.1 Ethical Standard

The study sites will ensure compliance with the legal and ethical obligations for the conduct of clinical research involving human subjects, with the key regulations and ethical standards implemented as follows:

- Title 21 CFR 50, Subpart A: General Provisions and Subpart B: Informed Consent, FDA
- Title 21 CFR 56, Subparts A-E: Institutional Review Boards
- FDA Information Sheets: Guidance for IRBs and Clinical Investigators, 1998 Update
- International Conference on Harmonisation GCP (ICH E6 R1): Consolidated Guideline, June 1996
- The Belmont Report

#### 11.2 Institutional Review Board

Prior to initiation of the study, the study protocol, investigator brochure, sample informed consent form, and any other documents that pertain to subject information and recruitment methods such as advertisements, will be submitted to a centralized and/or local IRB. Any other information that may be requested by the IRB for review and approval will also be submitted.

Approval from the IRB for all subsequent protocol amendments and changes to the informed consent form will be obtained. The IRB will be notified of protocol deviations as well as AEs and SAEs occurring at the site, in accordance with regulatory requirements.

Each IRB will review and approve the study protocol and subject informed consent form. After approval by the committee, the following documentation must be sent to the study manager or designee before the study commences:

- Confirmation of IRB approval of the protocol
- Confirmation of IRB approval of the informed consent form and applicable addenda
- A list of IRB members, their representative capacity, and their affiliation (a Health and Human Services General Assurance number will suffice)

#### 12 Informed Consent Process

The informed consent process will be initiated before a volunteer agrees to participate in the study and should continue throughout the individual's study participation. The subject will sign the informed consent document before any procedures are undertaken for the study. A copy of the signed informed consent/assent document will be given to the subject or the legal guardian for their records. The consent will explain that subjects may withdraw consent at any time throughout the course of the study. Extensive explanation and discussion of risks and possible benefits of this investigation will be provided to the subjects in understandable language. Adequate time will be provided to ensure that the subject has time to consider and discuss participation in the protocol.

The consent forms will describe in detail the study interventions/products/procedures and risks/benefits associated with participation in the study. The rights and welfare of the subjects will be protected by emphasizing that their access to and the quality of medical care will not be adversely affected if they decline to participate in this study.

### 12.1 Subject Confidentiality

Subject confidentiality is strictly held in trust by the participating Investigators, their staff, and the Sponsor and their agents. This confidentiality includes documentation, investigation data, subject's clinical information, and all other information generated during participation in the study.

No information concerning the study or the data generated from the study will be released to any unauthorized third party without prior written approval of the Sponsor and the subject.

The study monitor or other authorized representatives of the Sponsor or governmental regulatory agencies may inspect all documents and records required to be maintained by the Investigators, including but not limited to, medical records (office, clinic, or hospital) for the subjects in this study. The clinical study site will permit access to such records.

### 13 Confidentiality Policy

The information obtained during the conduct of this study is considered confidential and can be used by Evofem, Inc., for regulatory purposes and for the general development of the investigational product. All information supplied by Evofem, Inc., in connection with this study shall remain the sole property of Evofem, Inc., and is to be considered confidential information. No confidential information shall be declared to others without prior written consent from Evofem, Inc. Such information shall not be used except in the performance of this study. The information obtained during this study may be made available to other physicians who are conducting other clinical studies with the investigational product, if deemed necessary by Evofem, Inc.

### 14 Publication Policy

Evofem, Inc., is the IND Sponsor. Evofem, Inc., will assume responsibility for registering the study in the National Library of Medicine registry (https://www.clinicaltrials.gov). In compliance with Public Law 110-85, the FDA Amendments Act of 2007 (FDAAA), Evofem, Inc., will also post results of the study.

## 15 Summary of Changes

Table 3 Summary of Changes

| Version | Effective   | Summary of Changes   |  |
|---------|-------------|--|--|
| Number  | Date        |  |  |
| 1.0     | 24 Mar 2017 | Original protocol  |  |
| 2.0     | 19 Sep 2017 | Editorial changes and additional detail added throughout               |  |
|         |             | Title Page – added CRO information, updated AMPHORA name               |  |
|         |             | Signature page for the Investigator added                              |  |
|         |             | Original Section 2 – Protocol Summary changed to Protocol              |  |
|         |             | Synopsis, updated, and moved to front for easier reference             |  |
|         |             | Original section 3 – removed (included elsewhere in study              |  |
|         |             | documentation)   |  |
|         |             | Original Section 4.3 – removed (included in Investigator's             |  |
|         |             | Brochure)  |  |
|         |             | Sections renumbered  |  |
|         |             | Original Section 5; new Section 2 – added requirement for              |  |
|         |             | subjects to be treated to the clinical site's standard of care for STI |  |
|         |             | prevention including condom provision                                  |  |
|         |             | Original Section 6.2; new Section 3.2 – added/revised exclusion        |  |
|         |             | criteria 2, 3, 4, 5, 13, 16  |  |
|         |             | Original Section 6.4; new section 3.4 – revised randomization          |  |
|         |             | scheme to include IWRS   |  |
|         |             | Original Section 6.6.1; new Section 3.6.1 – clarified/expanded         |  |
|         |             | reason for withdrawal  |  |
|         |             | New Section 3.7 – added completer criteria                             |  |
|         |             | Original Section 7.1; new section 4.1 – updated the description of     |  |
|         |             | AMPHORA, removed intellectual property information                     |  |
|         |             | Original Section 7.1.5; new Section 4.1.5 – clarified amount of        |  |
|         |             | study product to be dispensed at each visit                            |  |
|         |             | Original Section 8.8; new Section 5.8.1 – revised list of              |  |
|         |             | procedures performed   |  |
|         |             | Original Section 8.8; new Section 5.8.3, 5.8.4, 5.8.5 – added          |  |
|         |             | requirement for subjects to abstain from intercourse 24 hours prior    |  |
|         |             | to the visit; removed condom issuance                                  |  |
|         |             | Original Section 9.2; new Section 6.2; removed "Pre-intervention       |  |
|         |             | adverse event" definition  |  |
|         |             | Original Section 9.4.1 – removed (duplicative)                         |  |

| **      | 77.00       |   |  |  |
|---------|-------------|---|--|--|
| Version | Effective   | Summary of Changes  |  |  |
| Number  | Date        |   |  |  |
|         |             | Original Section 9.6.2; new Section 6.6.2 – clarified pregnancy reporting process       |  |  |
|         |             | Original Section 7 – removed (not necessary due to extensive prior clinical testing)    |  |  |
|         |             | Original Section 11.2; new Section 8.2 – increased sample size to 844 subjects          |  |  |
|         |             | Original Section 11.3 – removed (not necessary)   |  |  |
|         |             | Original Section 11.4.3; new Section 8.3.3 – clarified evaluable subjects               |  |  |
|         |             | Original Section 11.5.3; new Section 8.4.3 – clarified exploratory analyses             |  |  |
|         |             | Appendix A – Schedule of Events changed to Schedule of                                  |  |  |
|         |             | Assessments, updated, and moved to front for easier reference                           |  |  |
|         |             | Appendix B – removed (included in Investigator's Brochure)                              |  |  |
| 2.1     | 10 Oct 2017 | Inclusion criterion #7 and exclusion criterion # 15 were updated to                     |  |  |
|         |             | provide clarity on acceptable forms of contraception                                    |  |  |
|         |             | Section 5.1 – removed statement regarding ICH GCP                                       |  |  |
|         |             | Section 6.6.2 – included definition of women of childbearing                            |  |  |
|         |             | potential   |  |  |
| 3.0     | 11 Oct 2017 | Inclusion criterion #7 and exclusion criterion #15 were updated to                      |  |  |
|         |             | provide clarity on acceptable forms of contraception                                    |  |  |
|         |             | Section 5.1 – removed statement regarding ICH GCP                                       |  |  |
|         |             | Section 6.6.2 – included definition of women of childbearing                            |  |  |
|         |             | potential   |  |  |
| 4.0     | 15 Mar 2018 | Inclusion criterion #1, age increased from 18-35 to 18-45                               |  |  |
|         |             | Exclusion criterion #2 (consume on average more than three                              |  |  |
|         |             | drinks of an alcoholic beverage) was merged with exclusion                              |  |  |
|         |             | criterion #3 (in the opinion of the investigator, has a history of                      |  |  |
|         |             | substance or alcohol abuse within that last 12 months                                   |  |  |
|         |             | Inclusion criterion #7 modified   |  |  |
|         |             | Exclusion criterion #15 may use NuvaRing  |  |  |
|         |             | Screening period increased from to 30-45 days   |  |  |
|         |             | Sites increased to 50   |  |  |
|         |             | Addition of exploratory measures (subject satisfaction, sexual satisfaction, SFQ, FSFI) |  |  |
|         |             |   |  |  |

| Version | Effective   | Summary of Changes   |
|---------|-------------|--|
| Number  | Date        | , g  |
| 5.0     | 13 Aug 2018 | Exclusion criterion #11, antibiotic treatment increased to 21 days |
|         |             | prior to enrollment to provide consistency throughout the protocol |
|         |             | Screening eligibility, increase from 30-45 days modified for       |
|         |             | consistency  |
|         |             | Study schedule, location of Schedule of Assessments table          |
|         |             | clarified  |
|         |             | Inclusion Criterion #7 modified for consistency throughout the     |
|         |             | protocol   |
|         |             | Exclusion Criterion #9 modified for consistency throughout the     |
|         |             | protocol   |
|         |             | Prohibited medications, antibiotic treatment increased to 21 days  |
|         |             | to provide consistency throughout the protocol                     |
|         |             | Appendix D, extra page removed                                     |
| 6.0     | 21 Jan 2019 | Table 1 Schedule of Assessments and Section 3.6.2, clarified that  |
|         |             | procedures for V5 should be followed for Early Termination.        |
|         |             | Added CT/GC NAAT testing is not required at V5/Early               |
|         |             | Termination if termination from the study is due to positive       |
|         |             | CT/GC NAAT test.   |
|         |             | Inclusion Criterion #9 clarified and formatting/numbering          |
|         |             | corrected.   |
|         |             | Section 3.6 clarified that positive CT/GC NAAT test at enrollment  |
|         |             | is a reason for withdrawal.  |
|         |             | Section 5.8.3 updated Termination Visit procedures for positive    |
|         |             | CT/CG testing at enrollment.                                       |
|         |             | Section 5.8.6 updated self-collected vaginal swab for CT and GC    |
|         |             | NAATs not required for Post-Intervention Follow-up Visit if        |
|         |             | termination of study is due to positive CT/GC NAAT test.           |
|         |             | Section 6.4.1 SAE causality – returned to original language.       |
|         |             | Safety CRO changed to ICON GPHS throughout.                        |

### 17 Appendices

### Appendix A. Grading of Study-related Adverse Events

The table referenced below is a modification of the NCI Common Terminology Criteria for Adverse Events (v4.03, May 2009) tables, adjusted to display common AEs applicable to this study. A grading (severity) scale is provided for each AE term. A brief definition is provided to clarify the meaning of each AE term. Any clinical event deemed by the clinician to be serious or life threatening should be considered a Grade 4 event.

A semi-colon indicates 'or' within the description of the grade; a single dash (-) indicates a grade is not available. ADL = Activities of Daily Living.

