#### **Serious Adverse Event (SAE)**

An SAE is any adverse event that results in any of the following outcomes:

- Death
- Life-threatening (immediate risk of death)
- Inpatient hospitalization or prolongation of existing hospitalization
- Persistent or significant disability or incapacity
- Congenital anomaly/birth defect

• Important medical events that may not result in death, be life-threatening, or require hospitalization may be considered an SAE when, based upon appropriate medical judgment, they may jeopardize the subject and may require medical or surgical intervention to prevent one of the outcomes listed in this definition

The term "life-threatening" in the definition of SAE refers to an event in which the subject was at risk of death at the time of the event. It does not refer to an event which hypothetically might have caused death if it were more severe.

The term "hospitalization" describes a period of at least 24 hours. Overnight stay for observation, treatment at an emergency room or treatment on an outpatient basis does not constitute a hospitalization. However, medical judgment must always be exercised and when in doubt the case should be considered serious.

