### 6.4 Investigator's Assessment of Adverse Events

The determination of seriousness, severity, and causality will be made by a site Investigator.

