#### **Seriousness**

An SAE is defined as any untoward medical occurrence that at any dose:

- Results in death
- Is life-threatening; this means that the subject is at risk of death at the time of the event, and it does not mean that the event hypothetically might have caused death if it were more severe
- Requires inpatient hospitalization or prolongation of existing hospitalization
- Results in persistent or significant disability or incapacity
- Is a congenital anomaly or birth defect
- Is an important medical event that may not be immediately life-threatening or result in death or hospitalization but that may jeopardize the subject or require intervention to prevent one of the above outcomes; examples of such events are intensive treatment in an emergency room or at home for allergic bronchospasm, blood dyscrasias or convulsions that do not result in hospitalization, or development of drug dependency or drug abuse

Medical and scientific judgment should be exercised in deciding whether a case is serious and whether expedited reporting is appropriate.

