#### **Intensity**

Investigators should assess the severity of AEs according to Common Terminology Criteria for Adverse Events (CTCAE) version 4.03. In general, CTCAE severity grades are:

- Grade 1: mild; asymptomatic or mild symptoms; clinical or diagnostic observations only; intervention not indicated
- Grade 2: moderate; minimal, local, or noninvasive intervention indicated; limiting ageappropriate instrumental activities of daily living (ADL) (instrumental ADL refer to preparing meals, shopping for groceries or clothes, using the telephone, managing money, etc)
- Grade 3: severe or medically significant but not immediately life-threatening; hospitalization or prolongation of hospitalization indicated; disabling; limiting self-care ADL (self-care ADL refer to bathing, dressing and undressing, feeding self, using the toilet, taking medications, and not bedridden)
- Grade 4: life-threatening consequences; urgent intervention indicated

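### Appendix A makes any serious event Grade 4, while 6.4.1 puts hospitalised or disabling events at Grade 3, so such events can be graded one too high

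*Protocol*

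**What the plan says.** Protocol 6.4 lists seriousness and severity as separate judgements: "The determination of seriousness, severity, and causality will be made by a site Investigator". Section 6.4.1 then handles them under separate sub-headings.

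Under Seriousness, the criteria include "Requires inpatient hospitalization or prolongation of existing hospitalization" and "Results in persistent or significant disability or incapacity", as well as an event that "Is an important medical event that may not be immediately life-threatening or result in death or hospitalization" but may jeopardise the subject or need intervention. The SAE definition in 6.2 has the matching item, "Inpatient hospitalization or prolongation of existing hospitalization".

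Under Intensity, severity follows CTCAE v4.03. The two grades that matter here are "Grade 3: severe or medically significant but not immediately life-threatening; hospitalization or prolongation of hospitalization indicated" (the entry goes on to cover disabling events) and "Grade 4: life-threatening consequences; urgent intervention indicated". Grade 5 is death.

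Appendix A adds one sentence that cuts across this: "Any clinical event deemed by the clinician to be serious or life threatening should be considered a Grade 4 event". Its key explains that a semicolon between descriptors means 'or' and that a dash means the grade does not exist for that term. Its general scale, for abnormalities without their own row, repeats the 6.4.1 wording for Grades 3 and 4.

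**The concern.** Seriousness is a regulatory classification by outcome, and severity is a rating of intensity. The Appendix A sentence sets the second from the first. Its life-threatening limb adds nothing, because such events are Grade 4 already. All of its new effect comes from the word *serious*, which the protocol defines broadly: 6.2 tells investigators to call an event serious when in doubt, and 6.4.2 says any event that recovers with sequelae should be rated an SAE.

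What is at stake is the grade in the safety tables. Protocol 8.4.2 and SAP 8.9.1 summarise adverse events by severity, and SAP 8.9.1 keeps only the highest severity per subject and event, so a raised grade replaces the correct one. If some sites follow the sentence and others follow the scale, the same event would carry different grades.

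**Working it through.** No power or sample-size arithmetic applies. The check sets each seriousness criterion in 6.4.1 against its grade under the 6.4.1 Intensity scale and under the Appendix A sentence, with *serious* read as the protocol defines it. Shift = 4 − (6.4.1 grade).

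| Seriousness criterion | Grade by 6.4.1 | Grade by the sentence | Shift |
|---|---|---|---|
| Hospitalisation, not life-threatening, no urgent intervention indicated | 3 | 4 | 4 − 3 = +1 |
| Disability, same conditions | 3 | 4 | 4 − 3 = +1 |
| Life-threatening | 4 | 4 | 4 − 4 = 0 |
| Death | 5 | 4, read literally | 4 − 5 = −1 |
| Important medical event | usually 3 or 4 | 4 | usually +1 or 0 |
| Congenital anomaly | depends on the event | 4 | depends on the event |

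Of the six criteria, two move up, one is unchanged, one moves down on a literal reading, and two depend on the event: 2 + 1 + 1 + 2 = 6.

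Two qualifications apply to the first two rows. A hospitalised or disabling event for which urgent intervention is indicated is already Grade 4, because the semicolon means 'or', and it does not move. The conflict also sits inside Appendix A itself, since its general scale has the same Grade 3 entry as 6.4.1.

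**Named terms.** The table lists four: vaginal inflammation, pain, burning and pruritus. For pain and pruritus the Grade 4 cell is a dash, so the sentence can assign a grade that the key says is unavailable for 2 of 4 terms. The burning cell is blank in the extracted text and is not counted. The contents page lists a separate Appendix B whose heading does not appear in the text supplied, so these rows may formally sit there. The clash with the key is the same either way.

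**Where the grade goes next.**
- The by-severity summaries are affected. SAP 8.9 specifies no statistical tests for safety, and SAP section 1 puts the table templates in a separate document, so the layout cannot be checked.
- A move from 3 to 4 leaves the grade-3-or-higher triggers in 6.5 unchanged.
- The 24-hour notice for cutaneous events in 6.5 adds nothing for serious events, because 6.1 already sends every SAE to the Medical Monitor within 24 hours.
- SAEs and deaths are summarised separately, without reference to grade.

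**The case against.** **Scope.** Section 6.5 points to Appendix A for anticipated study-related events, and the named terms are four local vaginal complaints. For severity in general, 6.4.1 sends investigators to CTCAE. This narrows the conflict but does not remove it: the sentence is not limited to the named terms, and the general scale beside it is for abnormalities outside them.

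**Lay meaning.** Section 6.4 gives the seriousness decision to the site Investigator, while Appendix A speaks of the clinician, so *serious* might be meant loosely as very severe. That is possible, and fewer events would then move. But it is a defined term in this protocol, and nothing signals another sense.

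**Deaths.** A reader might infer that fatal events will be recorded a grade too low. The documents do not support more than a literal clash: 6.4.1 gives Grade 5 for death, the table lists death as Grade 5 for vaginal inflammation, and 6.4.2 has a fatal outcome category. Most graders would probably use Grade 5.

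**Larger shifts.** A reader might also infer that moderate events would jump from Grade 2 to Grade 4 (4 − 2 = +2) and set off the 6.5 work-up. That group is close to empty. An important medical event will usually fit the medically significant wording of Grade 3 or the urgent-intervention wording of Grade 4. At Grade 3 or above the work-up is triggered anyway.

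**Conclusion.** The point holds as a narrow wording conflict. Events that are serious through hospitalisation or disability, with neither life-threatening consequences nor urgent intervention indicated, are Grade 3 by two texts and Grade 4 by a third. Where a site applies the sentence, such events are graded one too high. Grade 4 can also be assigned to two named terms that do not have it.

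This rests on *serious* having its protocol meaning and on a site giving the sentence priority over the scales. With no SAE rate in the documents, no count of affected events can be given.

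It would be wrong to infer that the safety conclusions or the trial result are at risk. The effect is on untested descriptive tables. Expedited reporting, the SAE and death summaries, and the efficacy analyses are untouched. This is worth correcting but minor.

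**What to change.** Delete 'serious or' from the Appendix A sentence. That alone is not enough: a fatal event would ordinarily also have been life-threatening and would still be caught literally, and Appendix A's general scale says that Grade 5 is not an option for some events. So also state that 6.4.1 (CTCAE v4.03) governs the grade, that death is Grade 5, and that seriousness is recorded separately. Check the grades of SAEs already recorded, including any deaths, before database lock. The SAP needs no change. The cost is a short protocol clarification and one round of grade queries.

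A separate small edit, independent of the sentence: the twice-weekly visit rule in 6.5 is written for cutaneous events that are Grade 3, which literally leaves out Grade 4. Change it to Grade 3 or higher.
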